2.4. Sample Size

The hypothesis of this study is that the slope of change in 6MWD from baseline to Week 72 (end of double-blind treatment period) will be 1.0 meter/week better in the ataluren arm than in the placebo arm, within a subset of subjects who are ≥ 7 to 16 years old with baseline 6MWD ≥ 300 meters and baseline time to stand from supine ≥ 5 seconds. The baseline 6MWD is defined as the maximum of the 6MWDs from a valid 6MWT on Day 1 and Day 2. Similarly, the Week 72 6MWD is defined as the maximum of the 6MWDs from a valid 6MWT on Day 1 and Day 2 of the Week 72 visit (end of double-blind treatment period). With a 1:1 randomization, 154 subjects will be required (77 subjects in the ataluren treatment arm and 77 subjects in the placebo arm) to detect a difference of 1.0 meter per week between ataluren and placebo with 85% power (two-sided $\alpha = 0.05$), assuming a common standard deviation of 2.058 meters per week. Further assuming a premature discontinuation rate of $\sim 5\%$, a total of 162 subjects (81 subjects in the ataluren treatment arm and 81 subjects in the placebo arm) will be enrolled for the primary endpoint analysis. The study is expected to enroll ~ 340 subjects overall, including those outside of the primary analysis population.

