6.1.3.2. ITT and PP Populations

As a supportive analysis, the primary MMRM analysis will be repeated using both the ITT and PP populations. In addition, the ANCOVA model after MI will also be repeated for ITT population. The baseline time to stand from supine (<5 seconds, ≥ 5 seconds) will be included in the testing model in the ITT analysis.

6.1.3.3. *Modification of mITT Criteria (+/- 15%)*

As supportive analyses, separate MMRM models similar to the primary analysis will be used to evaluate the change in 6MWD from baseline to Week 72 for all subjects with a baseline 6MWD ≥ 255 meters (ie, -15% from the 6MWD ≥ 300 meter lower bound) or baseline 6MWD ≥ 345 meters (ie, +15% from the 6MWD ≥ 300 meter lower bound)) and who also meet the age and stand from supine criteria for the mITT population (ie, 7 to 16 years old and time to stand from supine ≥ 5 seconds at baseline).

6.1.3.4. *Checking Missing at Random Assumption*

For the primary analysis, an additional sensitivity analysis will be employed to check the MAR assumption underlying the MMRM model where the reason for drop-out is considered. Subjects with following discontinuation reasons will be imputed using MI method using subjects in placebo arm who completed double-blind period of the study without missing values.

- Adverse event
- Withdrew consent
- Investigator decision

This analysis will be performed for mITT population. Detailed method and SAS codes are described in [Appendix 3](#).

6.1.3.5. *Using Average of Day 1 and Day 2 6MWDs Rather than Maximum*

The primary analysis uses the maximum of valid Day 1 and Day 2 6MWDs for baseline and Week 72. As a sensitivity analysis, the same analysis will be repeated with the average of valid Day 1 and Day 2 6MWDs for baseline and Week 72 for mITT population. For this analysis, the actual week for Baseline and Visit 8 will be calculated based on the first day of the visit.

6.1.3.6. *Assess the Impact of COVID19*

To assess the impact of COVID19, a sensitivity analysis will be performed similarly to the primary MMRM analysis and ANCOVA analysis after MI by removing all COVID19 impacted visits (as collected on CRF) for mITT and ITT populations. The baseline time to stand from supine (<5 seconds, ≥ 5 seconds) will be included in the testing model in the ITT analysis.

6.1.3.7. *Assess the Impact from Potential Correlation among Siblings*

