6.2. Secondary Efficacy Variables

6.2.1. Key Secondary Efficacy Variables

6.2.1.1. *Timed Function Tests - Composite Scores*

The rate of change over 72 weeks (slope) in composite TFT scores will be considered as the first key secondary efficacy endpoint. The composite TFT scores will be defined as the average in times to run/walk 10 meters, climb 4 stairs, and descend 4 stairs. The change in composite TFT scores will be analyzed using the same MMRM model used for the primary analysis with factors of baseline concomitant corticosteroid type (deflazacort, prednisone/prednisolone), baseline 6MWD category (<300 meters, 300 to <350 meters, 350 to <400 meters, \geq 400 meters), treatment, visit, the average time in the three timed function tests at baseline, interaction of visit and treatment, and the interaction of week and baseline average time. The slope will be compared between ataluren and placebo, and the estimated difference in the change at Week 72 will also be provided to facilitate interpretation.

Subjects who cannot perform a timed function test within 30 seconds, including those who is LoA or the timed function test is above 30 seconds, will be assigned a value of 30 seconds for the respective test for calculating the average change in times. Similarly to the primary analysis, if the average time of the 3 TFT tests is 30 seconds for multiple visits for a subject, the 30 seconds will be kept for the first visit with the assessment of 30 seconds, and set for missing for all visits afterwards.

If the test of the primary endpoint is statistically significant, then this key secondary endpoints will be tested at the 0.05 (two-sided) significance level.

As supportive analyses, the same analysis will be repeated:

- ANCOVA based on mITT population after MI
- MMRM model based on ITT population with additional factor of the baseline time to stand from supine (<5 seconds, ≥ 5 seconds) in the model
- ANCOVA based on ITT population after MI (with additional factor of the baseline time to stand from supine (<5 seconds, ≥ 5 seconds) in the model)

The change from baseline in composite average of timed function will be summarized by visit for mITT and ITT populations, and for subgroups below for mITT and ITT populations:

- Region (North and Latin America, Europe, Asia Pacific)
- Stop codon (UAA, UAG, UGA)

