Table 1 shows the estimated mean treatment difference from descriptive statistics (arithmetic mean), the prespecified linear regression MMRM model and ANCOVA (prespecified sensitivity analysis model) as well as the modified MMRM model with study time as a categorical variable.

Table 1: Estimated Treatment Difference for Change from Baseline in 6MWD at Week 72 (mITT Population – Double-blind Period)

| Model | Estimated treatment difference (SE) (Ataluren – Placebo) | |
|--------------------------|---|---|
| | Change from Baseline at Week 72 (meters) | Average rate of change from baseline in 6MWD over 72-week double-blind period (meters/week) |
| Descriptive statistics | 8.99 | 0.12 |
| MMRM (linear regression) | 9.95 (14.9) | 0.14 (0.207) |
| ANCOVA after MI | 9.10 (13.1) | 0.13 (0.182) |
| MMRM (categorical) | 8.26 (9.1) | 0.11 (0.126) |

SE = standard error

Sources: Table 14.2.1.1.1, Table 14.2.1.1.2, Table 14.2.1.1.18, Table 14.2.1.3.1.

Although the prespecified linear regression MMRM model gives a somewhat larger estimate of treatment difference, and the modified categorical MMRM model a somewhat smaller more conservative estimate of treatment effect, the estimates from all models are quite similar and close to the descriptive statistics.

Comparing the precision (SE) of the estimates the linear regression MMRM (which utilizes all seven data points collected for each subject during the double-blind period) does not yield the expected gain in efficiency compared to the simpler ANCOVA model which utilizes only Baseline and Week 72 observations and excludes all intermittent observations. The modified MMRM model with categorical 'visit time' yields the expected gain in efficiency with the standard error of the estimates being reduced with about 30% compared to the ANCOVA model.

In conclusion, the MMRM categorial model with visits being specified as a categorical variable, and otherwise following the exact specification of the planned linear regression MMRM model, fit the data the best and provides the most conservative and precise estimate of treatment. Therefore, the linear regression MMRM model was replaced with the categorical MMRM model for all endpoints where this model was prespecified.

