3.1.2. Supportive/Sensitivity Analyses

To confirm the robustness of the conclusions from the analyses performed on the ITT analysis set additional sensitivity analyses were added as detailed below.

3.1.2.1. *Analysis of Covariance (ANCOVA) Using Multiple Imputation (MI)*

The ANCOVA analysis using MI that was prespecified in SAP for the double-blind portion of Study 041 is still considered as a sensitivity analysis based on ITT population.

3.1.2.2. *Checking Missing at Random Assumption*

An additional sensitivity analysis is planned to check the MAR assumption underlying the MMRM categorical model where the reason for drop-out is considered based on ITT population. Subjects with following discontinuation reasons are to be imputed with MI method using subjects in placebo arm who completed double-blind period of the study without missing values.

- Adverse event
- Withdrew consent
- Investigator decision

3.1.2.3. *Using Average of Day 1 and Day 2 6MWDs Rather than Maximum*

The primary analysis uses the maximum of valid Day 1 and Day 2 6MWDs for baseline and Week 72 visits. As a sensitivity analysis, the same analysis is to be repeated with the average of valid Day 1 and Day 2 6MWDs for baseline and Week 72 visits for ITT population.

3.1.2.4. *Assess the Impact of Coronavirus Disease of 2019 (COVID19)*

To assess the impact of coronavirus disease of 2019 (COVID19), a sensitivity analysis is planned similar to the MMRM categorical analysis and ANCOVA analysis after MI by removing all COVID19 impacted visits (as collected on CRF) for ITT population.

3.1.2.5. *Assess the Impact from Potential Correlation among Siblings*

In this study, brothers participating in the study received the same treatment group designation to minimize potential compromise of the study drug blinding and to reduce the chance of dosing errors within families. In the primary analysis, siblings are considered as independent subjects. However, the assessments from two or more brothers may be highly correlated. To assess the impact of potential correlation among siblings, the MMRM categorical analysis are to be repeated by including only data from the first sibling for ITT population.

3.1.2.6. *Non-parametric analysis*

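### The slope MMRM was replaced wherever it was prespecified on linearity evidence from 6MWD in mITT alone, and the planned ITT slope analyses (6MWD, composite TFT) are missing from the revised list

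*SAP*

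**What the plan says.** The double-blind SAP (v1.0, 04 April 2022) makes the weekly slope of 6MWD in mITT the primary endpoint. It is estimated with a random-intercept, random-slope MMRM in actual week (Section 6.1.2), and the trial was sized on that slope, "to detect a difference of 1.0 meter per week between ataluren and placebo with 85% power" (Section 2.4). The same model was planned in ITT: "As a supportive analysis, the primary MMRM analysis will be repeated using both the ITT and PP populations" (Section 6.1.3.2). For the timed tests, Section 6.2.1.1 states: "The rate of change over 72 weeks (slope) in composite TFT scores will be considered as the first key secondary efficacy endpoint". It adds an ITT run of that model as a supportive analysis.

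The Changes from Planned Analysis document, written after the lock, reports in Section 2.1 that the decline in 6MWD was not linear. Its evidence is Figure 1 and Table 1, both for 6MWD in mITT. It concludes: "Therefore, the linear regression MMRM model was replaced with the categorical MMRM model for all endpoints where this model was prespecified". Section 3.1.1 then makes the categorical-visit MMRM in ITT the main analysis of 6MWD. Sections 3.2.1.1 and 3.2.2.2 do the same for composite TFT and the three single timed tests.

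Section 3.1.2 introduces its list of further analyses this way: "To confirm the robustness of the conclusions from the analyses performed on the ITT analysis set additional sensitivity analyses were added as detailed below". The list contains ANCOVA after multiple imputation, a missing-at-random check, Day 1/Day 2 averages, removal of COVID-19 visits, first sibling only, and a stratified Wilcoxon test. For the timed tests, ANCOVA after imputation is the only alternative model listed.

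**The concern.** The evidence is narrower than the decision. ITT adds boys under 7 or over 16, boys walking less than 300 m, and boys who stand from supine in under 5 seconds. Protocol Sections 11.2.3 to 11.2.5 describe these boys as following different courses: improving, slower, at high near-term risk of losing ambulation, or stable. Curvature in mITT therefore says little about curvature in ITT, and curvature in walking distance says little about timed tests capped at 30 seconds.

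The planned ITT slope analyses would show whether an ITT conclusion depends on a model chosen with the data in view, and they are not listed. Every MMRM re-run in Section 3.1.2 uses the new model. A reader of the ITT results then has no direct comparison between what was planned and what was adopted, at the point where ITT becomes the population of interest.

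**Working it through.** **1. Plan and revision side by side**

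| Analysis | Double-blind SAP v1.0 | Changes document | Linearity shown | Slope result listed |
|---|---|---|---|---|
| 6MWD, mITT | Slope, primary (6.1.2) | Replaced (2.1) | Yes (Figure 1) | Yes (Table 1) |
| 6MWD, ITT | Slope, supportive (6.1.3.2) | Categorical, main (3.1.1) | No | No |
| Composite TFT, mITT | Slope, first key secondary (6.2.1.1) | Replaced by 2.1, but preplanned mITT analyses kept end-of-text by 3.6 | No | Unclear |
| Composite TFT, ITT | Slope, supportive (6.2.1.1) | Categorical, main (3.2.1.1) | No | No |
| Single timed tests | Ambiguous (6.2.2.2 names both visit and week; the opening of Section 6 makes actual week the default) | Categorical (3.2.2.2) | No | No |
| rNSAA, ITT | Categorical (6.2.1.2) | Unchanged (3.2.1.2) | Not needed | Not applicable |

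**2. Reproducing the document's own figures (Table 1, 6MWD, mITT)**

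- Stated SE reduction against ANCOVA, about 30%: 1 − 9.1/13.1 = 30.5%. Reproduced.
- Metres divided by 72 weeks: slope 0.138 (SE 0.207), ANCOVA 0.126 (0.182), categorical 0.115 (0.126). These agree with the printed column within rounding.

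**3. What the switch did in the one case shown**

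z = estimate/SE, with a two-sided normal p:

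- Slope: 9.95/14.9 = 0.67, p = 0.50
- ANCOVA after imputation: 9.10/13.1 = 0.69, p = 0.49
- Categorical: 8.26/9.1 = 0.91, p = 0.36

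The SE fell by 1 − 9.1/14.9 = 38.9% against the slope model, and the estimate fell by 1.69 m. The z ratio is 0.908/0.668 = 1.36. The document describes the categorical estimate as the most conservative. That is true of the point estimate but not of the test statistic.

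**4. Illustration for ITT**

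No ITT estimate or SE is given, so the ITT slope result cannot be computed. Assume the mITT SE ratio, 9.1/14.9 = 0.61, carries over. The categorical z needed for the slope model to reach 1.96 is then:

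- Equal estimates: 1.96 × 14.9/9.1 = 3.21, which is p ≈ 0.0013
- mITT estimate ratio also carried over: 1.96 × (14.9/9.1) × (8.26/9.95) = 2.66, which is p ≈ 0.008

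On the same assumptions, a categorical p of 0.05 corresponds to a slope-model p of 0.23 (equal estimates) or 0.15 (estimate ratio carried over).

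**5. What else changed**

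Section 2.1 says nothing in the MMRM changed apart from how visit time enters. Comparing double-blind SAP 6.1.2 with Changes 3.1.1 shows four further differences:

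- Visits after loss of ambulation go from missing (after a first 0 m) to 0 m throughout.
- The random slope is dropped, and an unstructured visit covariance is added.
- Actual week becomes analysis visit. SAP 4.10 had chosen actual week to limit the effect of out-of-window COVID-19 visits.
- The response becomes change from baseline.

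The documents do not say which of these the categorical row of Table 1 includes.

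**The case against.** A categorical-visit MMRM is a standard model, was already prespecified as a sensitivity analysis for rNSAA, and does not force a straight line on the data. The planned primary slope result is disclosed beside its replacement in Table 1. The ITT analyses sat outside the fixed testing sequence of SAP 4.6. ANCOVA after imputation was prespecified in ITT for 6MWD and composite TFT and is kept; it and the Wilcoxon test depend on neither MMRM. In Table 1 the ANCOVA z (0.69) lies beside the slope model's (0.67), so it does expose the gain in precision.

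These points stand, and they rule out several stronger readings that a reader might infer:

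- *The slope model was dropped for every endpoint.* It was dropped only where prespecified. rNSAA, PUL, PROM, myometry and the time-to-event endpoints were never on it.
- *No prespecified ITT MMRM survives.* The categorical ITT model for rNSAA was prespecified and is kept.
- *The switch was the only post-lock decision.* The primary population, the loss-of-ambulation rule and the severity subgroups changed too.
- *Dependence on the switch is wholly hidden.* ANCOVA gives an indirect view, and Section 3.6 keeps the other preplanned mITT analyses end-of-text.
- *All three single timed tests plainly lost a prespecified slope model.* Section 6.2.2.2 is ambiguous, and the listed endpoints are changes to Week 72.

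The objection does not remove the gap. ANCOVA is a different model with different missing-data handling, and nothing says what follows if it and the categorical model diverge. Section 3.6 concerns mITT only. Disclosure of the mITT 6MWD result says nothing about ITT or the timed tests.

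**Conclusion.** The point holds in this form: linearity was assessed for one endpoint in one population, the model was replaced more widely, and two prespecified ITT slope analyses (6MWD and composite TFT) are absent from the revised list. Their absence means the effect of the switch on the ITT results cannot be seen directly.

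The measured size is confined to mITT 6MWD, where precision rather than the estimate drove the change and neither model came near significance. The ITT thresholds of about 0.008 and 0.0013 rest wholly on carrying over a ratio from that one comparison and are illustrative. A reader might infer that any ITT finding is an artefact of the switch. The documents do not support that, because the direction and size of the effect in ITT are unknown.

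**What to change.** In the Changes from Planned Analysis document:

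1. Add to Sections 3.1.2 and 3.2.1.1 the prespecified ITT slope MMRM for 6MWD and composite TFT, run under SAP v1.0 rules. Report it beside the categorical model and ANCOVA in the format of Table 1. Do the same in 3.2.2.2 for the single timed tests if SAP 6.2.2.2, read with the opening of Section 6, is taken as a continuous-week model.
2. Show the Figure 1 comparison for each endpoint and population where the model is replaced. Until then, limit the Section 2.1 conclusion to 6MWD in mITT.
3. State that the side-by-side shows the total effect of the switch and not linearity alone, and correct the statement in 2.1 that nothing else in the model changed.
4. Reconcile Section 2.1 with Section 3.6 on whether the mITT TFT slope results are reported.

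No rule that both models must agree is needed, since a slope model whose linearity assumption fails should not hold a veto. A formal curvature test is not needed as a gate either, since applying one after unblinding would itself be data-driven selection.

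The cost is small. The slope model has already been run for mITT 6MWD, so this means a few more table rows and figures. The downside is that some ITT results may look less favourable.

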3. CHANGE FROM PLANNED EFFICACY EVALUATION

3.1. Primary Efficacy Variable (6MWD)

There is no change in the primary efficacy endpoint, the mean rate of change from baseline in 6MWD over the 72-weeks of treatment. As explained in Section 2 the MMRM model was modified from a linear regression MMRM to a MMRM model with visit time as a categorical variable to account for the nonlinearity of study data.

3.1.1. Primary Analysis

The average rate of change from baseline in 6MWD over 72-weeks of treatment in the ITT population is considered the primary efficacy endpoint of interest for this study. The ITT population was specified in the original SAP as a supportive population for the primary endpoint analysis given its importance in providing information on the broad study population (N=359) encompassing the full range of age and ambulatory function. The MMRM category model with a random intercept, baseline 6MWD as a covariate, and factors of baseline concomitant corticosteroid type (deflazacort, prednisone/prednisolone), baseline 6WMD category (<300 meters, 300 to <350 meters, 350 to <400 meters, ≥400 meters), baseline time to stand from supine (<5 seconds, ≥5 seconds), treatment, visit (analysis visit as a categorical variable), interaction of visit and treatment, interaction of visit and baseline 6MWD, and unstructured covariance matrix (UN), is considered the primary analysis model of interest. In case of non-convergence, other types of covariance matrix are to be used in the order of heterogenous Toeplitz, Toeplitz, and compound symmetric. For this analysis, any subject who lose ambulation during the study was assigned a 6MWD of 0 meters for the first visit in which the subjects lose ambulation and set to 0 meters for all subsequent visits while they participate in the study. The average rate of change in 6MWD over 72-weeks of treatment is calculated from the estimated change from baseline in 6MWD at Week 72 from the MMRM categorical model.

A sample code is listed as below:

```
PROC MIXED data=<dataset> method=reml;  
  CLASS Cortico C6MWD TTSTBLC Subjid Trt AVISIT;  
  MODEL CHG6WMD = Cortico C6WMD TTSTBLC Trt B6WMD AVISIT  
                  AVISIT*B6WMD AVISIT*TRT/CL;  
  RANDOM Int / subject=Subjid;  
  REPEATED AVISIT / type=un subject=Subjid;  
  LSMEANS TRT*AVISIT / pdiff CL;  
RUN;
```

where

CHG6WMD = Change from baseline in 6WMD at each visit (Baseline to Week 72)
B6WMD = Baseline 6WMD
C6WMD = Baseline 6WMD category
Cortico = Baseline concomitant corticosteroid type
TTSTBLC = Time to stand from supine category
AVISIT = Analysis visits as categorical variable
Trt = Treatment group
Subjid = Subject

Int = Intercept

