8. CHANGES FROM THE PROTOCOL

Major changes to the planned analyses from the protocol are summarized as follows:

- NSAA total score will be calculated as the sum of the 16 scores (except for lifts head), instead of 17, based on Mayhew's publication [Mayhew 2013a].
- Slope of change in 6MWD over 144 weeks is removed from the list of secondary endpoints in section 2.3.2.
- Modified Intention-to-Treat (mITT) Population is removed from the list of study populations
- MMRM model was modified from a linear regression model to a MMRM model with visit time as a categorical variable to account for the nonlinearity of study data.

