4.6. Multiplicity Control

In order to control the family-wise error rate for the primary and key secondary efficacy endpoints, a fixed sequence procedure will be used. Testing orders of the primary endpoint and the key secondary endpoints are listed in the table below.

Table 1: Test Sequences

| |
|--|
| Primary Endpoint |
| Slope of change in 6-minute walk distance (6MWD) over 72 weeks (mITT) |
| Key Secondary Endpoints |
| (1) Slope of composite of average change in times to run/walk 10 meters, climb 4 stairs, and descend 4 stairs over 72 weeks (mITT) |
| (2) Change from baseline to Week 72 in North Star Ambulatory (NSAA) total score (mITT) |

Abbreviations: 6MWD, 6-minute walk distance; mITT, modified intention-to-treat; NSAA, North Star Ambulatory Assessment

The primary endpoint will be tested at the significance level of 0.05 (two-sided). If $p < 0.05$, then the primary endpoint will be considered statistically significant, and the study will be declared positive. If the test of the primary endpoint is statistically significant, then the key secondary endpoints will be tested in the order specified in the table above, each at the 0.05 (two-sided) significance level. Only if the first key secondary endpoint is statistically significant at the 0.05 significance level, the second key secondary endpoint will be tested also at the 0.05 significance level.

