1. OVERVIEW

This document details the changes and the rationales for the changes in the statistical methods in analyzing Study PTC124-GD-041-DMD (hereafter referred to as Study 041) from the planned analyses for **EMA/MHRA**.

This document is prepared on the basis of the final study protocol version 4.0 (dated 21JUL2020) and the final statistical analysis plan (SAP) version 1.0 (dated 04APR2022). The reasons for the changes are described in Section 2 and the detailed list of changes are given in Section 3.

The key changes made from the final SAP are summarized below:

- The assumption of constant (linear) decline in 6MWD over 72-week underpinning the prespecified linear regression MMRM model did not hold. The observed rate of decline was found to vary over time and between visits in the 72-week study period. To accurately account for this non-linearity the ‘visit time’ variable in the MMRM model was changed from a continuous (regression) variable to a categorical variable. The assessment for linearity and adjustment of the model were conducted in accordance with EMA guidance EMEA/CHMP/295050/2013 Section 7.4.
- Although there was a clear trend in favor of ataluren’s treatment effect in the predefined primary analysis subset (modified intention-to-treat, mITT), it did not fulfill its purpose as the most sensitive subset to capture significant benefit over the finite time period of a clinical trial. Therefore, the results for the full intention-to-treat (ITT) analysis set (a pre-specified supportive population for the primary endpoint analysis) will be presented in-text. Additional sensitivity analyses were added to confirm the robustness of the conclusions from the ITT analysis set (for details see Section 3).

[figure not shown]

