3.2. Secondary Efficacy Variables

3.2.1. Key Secondary Efficacy Variables

The key secondary efficacy endpoints remain the same as the prespecified endpoints, TFTs and rNSAA, with the primary population of interest being ITT and the primary analysis model of interest being the MMRM categorical model.

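### After the mITT primary test was not met, the changes document calls the ITT analysis primary without saying that it lies outside the SAP's fixed testing sequence

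*SAP*

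**What the plan says.** **Double-blind SAP.** For the primary and key secondary endpoints, section 4.6 says "a fixed sequence procedure will be used". The first test is "Slope of change in 6-minute walk distance (6MWD) over 72 weeks (mITT"), and "The primary endpoint will be tested at the significance level of 0.05 (two-sided"). The two key secondaries, the timed-function composite slope and the NSAA total score, are also in mITT, and each is tested only if the test before it succeeds. Section 6.1.2 repeats that the mITT slope is the primary endpoint, and section 2.4 sizes the trial on mITT. Section 6.1.3.2 repeats the analysis in ITT as supportive and gives it no alpha.

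**Changes from the planned analysis.** Section 2.1 reports that, once the data were examined after lock, the linear time assumption did not hold. Visit time therefore becomes categorical, and the section says the model is otherwise untouched. Section 1 says of mITT that "it did not fulfill its purpose as the most sensitive subset to capture significant benefit" and on that ground presents ITT in the text; section 3.6 repeats that mITT fell short. Section 3.1 opens with "There is no change in the primary efficacy endpoint". Section 3.1.1 then says that the rate of change "in the ITT population is considered the primary efficacy endpoint of interest for this study". Section 3.2.1 keeps the key secondaries, "with the primary population of interest being ITT and the primary analysis model of interest being the MMRM categorical model".

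Nothing in the published text of that document refers to the sequence in 4.6 or to the status of ITT p-values.

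**The concern.** A fixed sequence controls the family-wise error because the order of tests and the stopping point are set before results are known. Once the first test fails, everything after it is descriptive. Here the population carrying the word primary was replaced because the prespecified population had not shown a significant benefit, with the treatment differences already on the page. An ITT result read at 0.05 is then a second chance with no alpha behind it. The key secondaries are likewise read although the route to them had closed.

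The label is what is at stake. A reader who meets an ITT estimate called primary, next to a statement that the endpoint has not changed, has no prompt to go back to 4.6 and see that error-controlled testing ended with mITT.

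**Working it through.** **1. The plan's own figures.** Inputs from double-blind SAP 2.4: difference 1.0 m/week, SD 2.058, two-sided 0.05, power 85%.

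n per arm = 2 × (1.960 + 1.036)² × 2.058² / 1.0² = 2 × 8.978 × 4.235 = 76.05, so 77 per arm and 154 in total. The stated figure reproduces. For about 5% discontinuation, 154 × 1.05 = 161.7, which gives the stated 162.

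Table 1 of the changes document is also consistent: 9.95/72 = 0.138 and 14.9/72 = 0.207 m/week, matching its rate column after rounding.

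**2. The mITT result.** The document prints no p-values. From the Table 1 estimates and standard errors, z = estimate/SE with a two-sided normal p:

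| Model (mITT) | Week 72 difference (SE), m | z | p | 95% CI, m |
|---|---|---|---|---|
| Linear MMRM, prespecified | 9.95 (14.9) | 0.67 | 0.50 | −19.25 to 39.15 |
| ANCOVA after MI | 9.10 (13.1) | 0.69 | 0.49 | −16.58 to 34.78 |
| Categorical MMRM | 8.26 (9.1) | 0.91 | 0.36 | −9.58 to 26.10 |

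On the slope scale the prespecified interval is −19.25/72 to 39.15/72, that is −0.27 to 0.54 m/week. Its upper limit is below the planned 1.0 m/week.

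**3. Applying 4.6.** p = 0.50 exceeds 0.05, so the sequence stops and neither key secondary may be tested. No ITT test is in the sequence. mITT fails under every model in the table, so the change of population is the decisive step.

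**4. The statements of no change.** The two specifications side by side:

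| | Double-blind SAP 6.1.2 | Changes document 3.1.1 |
|---|---|---|
| Population | mITT | ITT |
| Response | 6MWD at each visit | Change from baseline at each visit |
| Time | Actual week, continuous | Analysis visit, categorical |
| Random effects | Intercept and slope | Intercept only, with an unstructured matrix across visits |
| Quantity compared | Slope | Week 72 change as a rate (8.26/72 = 0.11) |
| After loss of ambulation | Zero once, then missing | Zero at that and every later visit |

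The added factor for time to stand is not counted, because 6.1.3.2 already planned it for ITT.

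**5. Illustrative family-wise error.** Suppose there is no effect in either population and ITT is tested at 0.05 whenever mITT fails. The error is then 1 − P(|Z₁| < 1.96 and |Z₂| < 1.96), with correlation taken as √(n mITT / n ITT) for nested sets. Using the planned mITT size of 162 and the stated ITT size of 359, the correlation is √(162/359) = 0.67 and the error is 0.085. Other values:

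- correlation 0.9: 0.070
- correlation 0.5: 0.091
- independence: 1 − 0.95² = 0.0975

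**The case against.** Several things can fairly be said for the sponsor.

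- **The model.** Checking linearity is sound practice, and non-linearity is the stated reason for the new model. That model lowers the mITT estimate from 9.95 to 8.26 m and does not rescue it. A reader might infer that the model, like the population, was chosen because the test failed. The documents give that reason only for the population. What remains is that the model was chosen after lock, on the data, with its smaller standard error (9.1 against 14.9) among the arguments for it.
- **ITT was planned as support.** The double-blind SAP already contains ITT analyses of 6MWD (slope MMRM and ANCOVA after MI, 6.1.3.2), of the timed-function composite (the same two methods, 6.2.1.1) and of rNSAA (ANCOVA after MI and categorical MMRM, 6.2.1.2). It would be wrong to call every ITT result post hoc.
- **Disclosure.** The changes and reasons are set out, the mITT 6MWD result stays in the text, and the other planned mITT results are kept at the end (3.6). No ITT p-value or claim of ITT significance appears. A reader might infer concealment or an altered trial conclusion. The clinical study report is not among the documents, and these pages do not show either.
- **Slope against Week 72 change.** In the planned linear model the Week 72 difference is simply 72 times the slope, so the overlap with the separate Week 72 secondary endpoint is a small matter.

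These points narrow the criticism. None of them gives ITT an alpha, and non-linearity is no reason to change the population.

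**Conclusion.** The point holds as a defect of labelling and error control. By the SAP's own rule the primary test was not met (p = 0.50) and confirmatory testing ended there. Calling ITT primary afterwards, and moving the key secondaries to it, without stating that these results are outside the sequence, is wrong as written. So are the statements in 2.1 and 3.1 that nothing else changed. An interval of −0.27 to 0.54 m/week does not support section 1's description of a clear trend.

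The mITT figures rest only on Table 1 and a normal approximation. The 8.5% is illustrative. The actual mITT size is not given, and the square-root correlation assumes the same model and equal variability in both populations, which is doubtful here. The fair range is 7.0% to 9.1%, with 9.75% under independence, all before counting the choice of model. The conclusion does not depend on that figure.

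A reader might also count the open-label SAP here, since its section 8 says "Modified Intention-to-Treat (mITT) Population is removed from the list of study populations". That is a separate, secondary matter. The open-label SAP has no primary endpoint and no multiplicity control, and it discloses the removal. The issue there is with Protocol 9.4.5.1 and 9.4.5.3, which call for both populations at the end of both phases.

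**What to change.** In the changes document:

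- State that the primary analysis remains the mITT slope test of double-blind SAP 6.1.2 and 4.6, that it was not met, and that the fixed sequence stopped there.
- Label the ITT analyses already prespecified as supportive, for example 6MWD ANCOVA after MI, and rNSAA ANCOVA after MI and categorical MMRM. Label the promotion of ITT to primary, and the categorical model for 6MWD and the timed function tests, as post hoc. Give all of these nominal p-values.
- Correct 2.1 and 3.1 to list what changed: population, response, random slope, quantity estimated, and values after loss of ambulation.
- Reconcile 3.2.1, which makes the categorical MMRM the main model for the key secondaries, with 3.2.1.2, which reports no change for rNSAA. The planned rNSAA test was ANCOVA after MI, with the categorical MMRM as its sensitivity analysis.

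The cost is wording only, with no new data or analyses. The stated conclusion becomes less favourable.
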